8.2.7 Important Protocol Deviations

An important protocol deviation (IPD) is a protocol deviation that has the potential to affect the interpretation of study results. IPDs will be identified from the clinical database and/or site deviation log.

The protocol deviations that may be considered as potential IPDs include, but are not limited to:

- Violation of subjects rights, safety or well-being
- Subject entered the study despite violation of any inclusion or exclusion criteria
- Subject received prohibited concomitant medications
- Subject received the wrong treatment or incorrect doses
- Subject remained in study despite meeting withdrawal criteria

All IPDs will be presented in an individual subject data listing.

8.3 Adherence Analysis

All analyses described in this section will be based on the FAS, unless specified otherwise. The analysis will include all available measurements through the last scheduled on-treatment visit (Week 48), including measurements after treatment discontinuation, per the visit windowing rules described in [Appendix B](#).

8.3.1 List of Analyzed Adherence Endpoints

This study was terminated early by a business decision. The data collected at the time of termination are limited and premature due to early termination. Therefore, we will perform the descriptive summary for the following applicable endpoints as described in Section 5.3.1:

- Mean percentage adherence to LUM/IVA treatment over any treatment duration for all subjects.
- Mean percentage adherence to LUM/IVA treatment over 0 through 12 weeks for subjects who have at least 12 weeks of eligible smart pill bottle data.
- Proportion of subjects with $\geq 80\%$ adherence over 0 through 12 weeks for subjects who have at least 12 weeks of eligible smart pill bottle data
- Proportion of subjects with $\geq 90\%$ adherence over 0 through 12 weeks for subjects who have at least 12 weeks of eligible smart pill bottle data

8.3.2 Analysis of Adherence Endpoints

Mean percentage adherence to LUM/IVA treatment over treatment duration for all subjects

The percentage adherence over treatment duration for each subject is defined as:

$$100 \times (\text{total number of smart bottle openings over the eligible treatment duration excluding the physician-directed interruption periods of the eligible treatment duration}) / [2 \times (\text{eligible duration of treatment} - \text{the number of physician-directed interruption days of the eligible treatment duration})]$$

Note: (1) the physician-directed interruption is defined as the reported interruptions due to reasons not being “Non-compliance”; (2) if there are more than 2 smart bottle openings at any day, they will be counted as 2 in calculation of the adherence endpoints. (3) the eligible treatment duration = eligible date of last dose – date of first dose + 1, where the eligible date of last dose is defined to be either the CRF collected date of last dose or the last activity date of smart bottle data, whichever is earlier.

Descriptive statistics will be provided by the number of subjects (n), mean, SD, SE, median, min, and max by treatment arm based on FAS. [REDACTED]

The percentage adherence will also be listed.

Mean percentage adherence to LUM/IVA treatment over 0 through 12 weeks for subjects who have at least 12 weeks of eligible smart pill bottle data

Subjects who have at least 12 weeks of eligible smart pill bottle data are defined as those who have at least 12 weeks of eligible treatment duration = eligible date of last dose – date of first dose + 1, where the eligible date of last dose is defined to be either the CRF collected date of last dose or the last activity date of smart bottle data, whichever is earlier.

The percentage adherence over 12 weeks for each eligible subject is defined as:

$$100 \times (\text{total number of smart bottle openings over the first 12 weeks excluding the physician-directed interruption periods of the first 12 weeks}) / [2 \times (12 \text{ weeks (ie, 84 days)} - \text{the number of physician-directed interruption days of the first 12 weeks})]$$

Note: (1) the physician-directed interruption is defined as the reported interruptions due to reasons not being “Non-compliance”; (2) if there are more than 2 smart bottle openings at any day, they will be counted as 2 in calculation of the adherence endpoints.

Descriptive statistics will be provided by the number of subjects (n), mean, SD, SE, median, min, and max by treatment arm based on FAS. [REDACTED]

The percentage adherence will also be listed.

In addition, the number of smart bottle openings during the physician-directed interruption periods will be presented in a by-subject listing. Please note that if there are more than 2 smart bottle openings at any day, they will be counted as the actual number in this listing.

Further exploratory analyses may be performed if deemed necessary and sufficient data is available.

Proportion of subjects with $\geq 80\%$ (or 90%) adherence 0 through 12 weeks for subjects who have at least 12 weeks of eligible smart pill bottle data

For each eligible subject, the percentage of adherence over 12 weeks will be calculated as described above. The proportion of subjects with $\geq 80\%$ adherence rate over 12 weeks and the proportion of subjects with $\geq 90\%$ adherence rate over 12 weeks will be presented in a summary table.

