### 7.2 Secondary Endpoints

- Mean percentage adherence to LUM/IVA treatment over 24 weeks
- Mean percentage adherence to LUM/IVA treatment from Week 25 through Week 48
- Proportion of subjects with  $\geq 80\%$  LUM/IVA adherence over 24 weeks
- Proportion of subjects with  $\geq 80\%$  LUM/IVA adherence over 48 weeks
- Proportion of subjects with  $\geq 80\%$  LUM/IVA adherence from Week 25 through Week 48
- Proportion of subjects with a non-physician-directed LUM/IVA interruption  $\geq 72$  hours over 48 weeks
- Number of non-physician-directed LUM/IVA interruptions  $\geq 72$  hours over 48 weeks
- Time to the first non-physician-directed LUM/IVA interruption  $\geq 72$  hours over 48 weeks

[REDACTED]

[REDACTED]

[REDACTED]

[REDACTED]

[REDACTED]

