### 12.3.1 General Considerations

All subject data, including those derived will be presented in subject data listings; listings will display all subjects who were randomized, regardless of whether or not they received LUM/IVA.

Continuous variables will be summarized using the following descriptive summary statistics: the number of subjects (n), mean, SD, standard error (SE), median, minimum value (min), and maximum value (max). The precision of the measurement for each continuous variable will be specified in the SAP.

**Categorical data** will be summarized using counts and percentages.

Unless specified otherwise, only descriptive analyses will be performed (i.e., no statistical hypothesis testing will be performed).

**Baseline** for a variable, unless otherwise specified, will be defined as the most recent nonmissing measurement (scheduled or unscheduled) collected at or before Day 1 of the study.

**Change from baseline** will be calculated as postbaseline value minus baseline value.

Rules for handling missing data will be described in the SAP.

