#### **12.3.2.4    Study Drug Exposure and Compliance**

Exposure to LUM/IVA (i.e., duration of treatment in days) will be summarized for the FAS in terms of duration of treatment a subject received (in days), defined as the last day minus the first day of LUM/IVA plus 1. Exposure will be summarized by study arms for the FAS.

Primary and secondary analyses of adherence will be performed through smart technology generated data. A complementary analysis based on pill count and missing/interruption of dose

will be conducted. Information on number of pills and drug interruption will be collected from dispensing pharmacy and subjects.

These pharmacy and subject reported compliance data will be summarized for the FAS and will be derived in at least 1 of 2 methods pending data availability:

(1) based on pill counts calculated as:

$$100 \times (\text{total number of tablets taken}) / (4 \times \text{duration of LUM/IVA exposure in days})$$

And/or:

(2) based on medication interruption days using the formula:

$$100 \times [1 - (\text{total number of days LUM/IVA interrupted} \geq 72) / (\text{duration of LUM/IVA exposure})]$$

Duration of treatment and dosing compliance will be summarized by means of descriptive summary statistics.

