**Table 13-3 Classifications for Study Drug Action Taken With Regard to an AE**

Classification	Definition
Dose not changed	LUM/IVA dose not changed in response to an AE
Dose reduced	LUM/IVA dose reduced in response to an AE
Drug interrupted	LUM/IVA administration interrupted in response to an AE
Drug withdrawn	LUM/IVA administration permanently discontinued in response to an AE
Not applicable	Action taken regarding LUM/IVA administration does not apply. “Not applicable” will be used in circumstances such as when the investigational treatment had been completed before the AE began and no opportunity to decide whether to continue, interrupt, or withdraw treatment is possible.

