8.2.6 Study Drug Compliance

Study drug compliance based on number of tablets will be assessed by calculating the percentage of tablets consumed relative to the expected number of tablets administered during the subject's actual time on-study. The expected number of tablets administered during the subject's actual time on-study will be 4 tablets per day multiply the number of days in the study. The number of tablets consumed is the difference between the expected number of tablets dispensed and the total number of tablets returned.

These pharmacy and subject reported compliance data will be summarized during the overall treatment duration (from first dose to last dose), based on the medication interruption days.

Compliance rate based on the interruption days will be calculated as follow:

$$100 \times [1 - (\text{total number of days of any study drug interruption}) / (\text{duration of study drug exposure})]$$

The total number of days study drug interrupted is defined as the total of number of days the study drug was interrupted in each interruption interval, where number of days study drug interrupted in each interval is defined as the interruption end date - the corresponding interruption start date + 1.

Study drug compliance will be summarized descriptively by the number of subjects (n), mean, SD, median, min, and max. They will also be summarized in categories: $<80\%$ and $\geq 80\%$ using frequency tables.

Study drug compliance summaries will be based on the FAS.

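### SAP 8.3.2 Note (1) counts every reported interruption not coded Non-compliance as physician-directed, so a gap no physician directed can leave the bottle-based adherence score unchanged

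*SAP*

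**What the plan says.** After early termination the SAP keeps four adherence endpoints (5.1, 8.3.1): mean percentage adherence over any duration, mean percentage adherence over the first 12 weeks, and the proportions at ≥80% and ≥90% over 12 weeks. In 8.3.2, physician-directed interruption days leave the denominator and openings on those days leave the numerator. Note (1), given for both means, supplies the definition: "the physician-directed interruption is defined as the reported interruptions due to reasons not being" *Non-compliance*. The two proportions reuse the 12-week score, so the rule reaches all four endpoints.

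The protocol uses the opposite term in three secondary endpoints, for example "Proportion of subjects with a non-physician-directed LUM/IVA interruption" of at least 72 hours (7.2), but its readable text never defines it. Protocol 12.3.2.4 gives the source of the interruption data: "Information on number of pills and drug interruption will be collected from dispensing pharmacy and subjects".

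Two other outputs bear on the point. SAP 8.2.6 summarises a tablet-count compliance rate with no interruption days removed, and an interruption-day rate based on the "total number of days of any study drug interruption". Both use the FAS and both get a table split at 80%. SAP 8.3.2 also says that "the number of smart bottle openings during the physician-directed interruption periods will be presented in a by-subject listing".

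**The concern.** Taking truly directed stops out of an adherence score is legitimate. The difficulty is that Note (1) defines them by what they are not. Any reason other than one label is treated as a physician's direction, although the information may come from the pharmacy or the subject. A subject who stops by choice and has the stop recorded under another reason is scored as if the gap had not occurred.

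This matters because the protocol's rationale (5.2) for the smart bottle is that self-report and objective measures disagree. Here a reported reason overrides the bottle record. At stake is whether the two means and the two proportions describe adherence over the whole period or only over the days left after an exclusion of unknown content.

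**Working it through.** The plan gives no figure for the effect of this rule, so there is none to reproduce.

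**Inputs from the documents.** An 84-day window, 2 openings expected per day, thresholds of 80% and 90% (SAP 8.3.2); 4 tablets expected per day (SAP 8.2.6).

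**Assumptions, not in the documents.** One reported gap of g days within the first 84 days, under a reason other than *Non-compliance*; no openings in the gap; adherence of b% on the other days.

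**Step 1, formulas.** Openings outside the gap number (b/100) × 2 × (84 − g).
- Note (1) score: 100 × openings / [2 × (84 − g)] = b, whatever the length of the gap.
- Score with the gap counted: 100 × openings / (2 × 84) = b × (84 − g)/84.

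**Step 2, where the thresholds are crossed.**

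| b (Note (1) score) | Gap, days | Score with gap counted |
|---|---|---|
| 100% | 8 | 76/84 = 90.5% |
| 100% | 9 | 75/84 = 89.3% |
| 100% | 16 | 68/84 = 81.0% |
| 100% | 17 | 67/84 = 79.8% |
| 95% | 4 | 95 × 80/84 = 90.5% |
| 95% | 5 | 95 × 79/84 = 89.3% |
| 95% | 13 | 95 × 71/84 = 80.3% |
| 95% | 14 | 95 × 70/84 = 79.2% |

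With perfect dosing otherwise, counting the gap puts the subject below 90% from 9 days and below 80% from 17 days. At 95% outside the gap, the crossings come at 5 and 14 days.

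**Step 3, what SAP 8.2.6 would show.** Take b = 100, a 17-day gap in the first 12 weeks, 168 days both on study and on drug (assumed), and all untaken tablets returned.
- Interruption-day rate: 100 × (1 − 17/168) = 89.9%.
- Tablet-count rate: 4 × 151 = 604 of 4 × 168 = 672, which is 89.9%.
- 12-week bottle score: 100% under Note (1), 79.8% with the gap counted.

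The 8.2.6 rates fall by 10.1 points and stay in the ≥80% category, while the 12-week score moves by 20.2 points and crosses 80%. If time on study and on drug ends at day 84, 8.2.6 gives 67/84 = 79.8%, the same as the recounted bottle score. In either case a stop that a physician did direct gives the same 8.2.6 figures, so those summaries cannot separate the two kinds of gap.

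**Step 4, the listing.** For a gap with no openings, where the score gains most, the listing of openings inside excluded periods shows zero. As described, it gives neither the number of excluded days nor the reasons.

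**The case against.** The strongest reply is that the report already contains adherence without the exclusion. A reader might infer from 8.3.2 that it does not; SAP 8.2.6 shows otherwise. In the tablet-count rate an untaken dose counts whether or not the gap was reported and however it was coded, provided the tablets are returned. A reader might also infer that these rates are not shown by arm. Section 8.2.6 does not say so itself, but it uses the FAS, and SAP 7 groups FAS subjects by the technology arm they actually received. Both replies stand. What they leave open is that 8.2.6 covers the whole treatment period with a different instrument and gives no 12-week or ≥90% figure.

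Second, the eCRF reason list is not available to us. *Non-compliance* may be the natural code for every subject-chosen stop, site staff enter the data, and the investigator answers for their accuracy (Protocol 13.3, 13.5). This also stands, and it makes the concern conditional.

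Third, text is redacted directly after the descriptive-statistics sentences for both means and may hold a further summary. The finding is limited to the readable text.

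Fourth, individual listings are planned ("All subject data, including those derived will be presented in subject data listings", Protocol 12.3.1), so a reader with access might rebuild the score by hand. That is possible, but it is not a stated summary.

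Fifth, scoring with no exclusion counts stops that the protocol itself requires (11.5.3) as missed doses. That is true, and it is why such a table belongs beside the main result and should not replace it.

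**Conclusion.** The point holds as a cheap improvement of minor severity. Note (1) is a stated rule, but it labels a residual category as physician-directed and takes it out of all four retained endpoints. For one subject over 84 days the rule can hold a score at 100% that would be under 90% from a 9-day gap and under 80% from a 17-day gap, given no openings in the gap and perfect dosing outside it.

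This concerns reported gaps only. Unreported gaps, and those coded *Non-compliance*, still lower the score.

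A reader might go further and infer that the reported adherence is inflated, or that the contrast between arms is biased. The documents do not support either. Without the reason list the effect may be nil. Arm A has alerts and site access to bottle data and Arm B has neither (Protocol Table 8-1), so equal gaps and equal coding are not assured, but nothing in the text says how coding would differ. Neither size nor direction can be derived. No hypothesis test is affected, because SAP 3 replaces the planned analyses with descriptive summaries.

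**What to change.** 1. In Note (1), replace the definition by exclusion with a list of the eCRF reasons that document physician or protocol direction. Apply it without reference to arm, and state how *other* and missing reasons are scored. An adverse-event action recorded as "LUM/IVA administration interrupted in response to an AE" (Protocol Table 13-3) does not say who decided, so it should not qualify on its own.
2. Add to SAP 8.3.2 one by-arm sensitivity table giving both means and the ≥80% and ≥90% proportions with no interruption days excluded, together with the number of excluded days by recorded reason and arm. Read it beside the tablet-count rate in 8.2.6.

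The cost is a wording change and one table from data already collected. The downside is that the sensitivity figures count truly directed stops as missed doses, so they are a bound and not a better estimate. They are a lower bound unless openings inside the excluded days run at a higher rate than outside: for example, 90% outside and 100% inside a 14-day gap gives (90 × 70 + 100 × 14)/84 = 91.7%, above the 90% that Note (1) reports. If the reason list shows that every subject-chosen stop is coded *Non-compliance*, stating that in Note (1) settles the matter.

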**Table 3-2 Treatment Period and Safety Follow-up Visit Assessments – Study VX15-809-114**

Event/Assessment	Day 1	Week 12	Week 24	Week 36	Week 48	Safety Follow-up Week 52 a
Clinic visit	X	X	X	X	X	X
Vital signs b	X	X	X	X	X	X
Physical examination c					X	X d
Liver Function Testing e	X	X	X	X	X	X
Urine pregnancy test (all female subjects of childbearing potential)	X	X	X	X	X	X
Randomization f	X					
Standardized education on adherence	X					
Concomitant medications, treatments, and procedures	X	X	X	X	X	X
Smart Adherence Technology-Reported Adherence g		X	X	X	X	

LUM/IVA drug count i		X	X	X	X	
Ophthalmologic examination j					X	
AEs and SAEs	Continuous from signing of ICF or assent (where applicable)					
LUM/IVA resupply	Every 3 months throughout study					

AE: adverse event; ICF: informed consent form; IVA: ivacaftor; IWRS: interactive web response system; LUM: lumacaftor; PE: physical examination; SAE: serious adverse event; [REDACTED]

a The Safety Follow-up Visit is 28 ( $\pm$  7) days after the last dose of LUM/IVA (Section 8.1.3).

b Vital signs will be assessed following a 5-minute rest in the seated or supine position.

c Symptom-targeted PEs will occur at any time during the study if triggered by AEs or if deemed necessary by the investigator.

d Required for subjects who do not begin commercial LUM/IVA after Week 48 only.

e Day 1 only blood draws will be collected before the first dose of LUM/IVA. Liver function testing (alanine aminotransferase [ALT], aspartate aminotransferase [AST], gamma-glutamyl transpeptidase [GGT], alkaline phosphatase [ALP], and total bilirubin) must be performed at the scheduled visits (Section 11.5.2).

f Randomization must occur after all inclusion and exclusion criteria are met and before the first dose of LUM/IVA. Randomization will be done through IWRS.

g Data will be collected for all subjects throughout the study in real-time. Subjects in Study Arm A will review data with physicians at study visits.

i LUM/IVA drug count will be collected at the end of specified study visits.

j See Section 11.5.6.

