**Table 10-1 LUM/IVA Administration**

All Subjects	Time	LUM/IVA (200/125 mg per tablet)
LUM 400 mg/IVA 250 mg q12h	AM	2 tablets
	PM	2 tablets

IVA: ivacaftor; LUM: lumacaftor; q12h: every 12 hours

LUM/IVA should be administered within 30 minutes of consuming fat-containing food such as a standard CF high-fat, high-calorie meal or snack. LUM/IVA should be administered q12h ( $\pm$  4 hours).

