### **10.5 Missed Doses**

If subjects miss a dose and recall the missed dose within 6 hours, they should take their dose with food. If more than 6 hours have elapsed after their usual dosing time, they should skip that dose and resume their normal schedule for the following dose.

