8 STATISTICAL ANALYSIS

8.1 General Considerations

The Schedule of Assessments is provided in [Appendix A](#).

Continuous variables will be summarized using the following descriptive summary statistics: the number of subjects (n), mean, standard deviation (SD), standard error (SE), median, minimum value (min), and maximum value (max).

Categorical variables will be summarized using counts and percentages.

Baseline value, unless specified otherwise, will be defined as the most recent non-missing measurement (scheduled or unscheduled) collected before the first dose of study drug.

Change (absolute change) from baseline will be calculated as postbaseline value minus baseline value

Treatment-emergent (TE) Period will be from the first dose date of the study drug to the Safety Follow-up Visit or 28 days after the last dose, whichever is latest. The TE period will be used for safety analyses.

Unscheduled visits: Unscheduled visit measurements will be included in analysis as follows:

- In scheduled visit windows per specified visit windowing rules.
- In the derivation of baseline/last on-treatment measurements.
- In the derivation of maximum/minimum on-treatment values and maximum/minimum change from baseline values for safety analyses.
- In individual subject data listings as appropriate.

Visit windowing rules: Day 1 is defined as the day of first dose of study treatment. Relative days after Day 1 are calculated as (assessment date – Day 1 date) + 1. Relative days prior to Day 1 are calculated as (assessment date – Day 1 date). The day prior to Day 1 is Day -1. The analysis visit windows for protocol-defined visits are provided in [Appendix B](#). Visit window rules will not apply to the smart technology-reported adherence, which will be collected and stored daily and will be summarized at actual date. Visit window rules will apply to other visit-dependent assessments, including liver function tests, and patient-reported, as well as, physician-reported outcomes.

Incomplete/missing data will not be imputed, unless specified otherwise.

Outliers: No formal statistical analyses will be performed to detect or remedy the presence of statistical outliers, unless specified otherwise.

Multiplicity: No multiplicity adjustment will be performed for hypothesis testing.

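### Counting bottle openings by calendar date can cost a fully adherent subject a count after an isolated, permitted after-midnight dose, and expects two openings on first and last dates where only one dose was possible

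*SAP*

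**What the plan says.** SAP 8.3.2 defines percentage adherence as 100 × counted openings / (2 × days). Three elements matter here.

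- **Cap.** Note (2) to both formulas says "if there are more than 2 smart bottle openings at any day, they will be counted as 2 in calculation of the adherence endpoints".
- **Days.** For the whole-duration endpoint, "the eligible treatment duration = eligible date of last dose – date of first dose + 1", where the last date is the earlier of the CRF last-dose date and the last bottle activity. For the 12-week endpoints the figure is fixed at 84 days. Both subtract physician-directed interruption days.
- **Date basis.** SAP 8.1 exempts from visit windowing the "smart technology-reported adherence, which will be collected and stored daily and will be summarized at actual date".

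No text defines a dosing day, moves an after-midnight opening back to the evening it belongs to, or prorates the first or last date.

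On dose timing, Protocol Table 10-1 says "LUM/IVA should be administered q12h", with a tolerance of 4 hours either side. Protocol 10.5 adds: "If subjects miss a dose and recall the missed dose within 6 hours, they should take their dose with food". For Day 1, Protocol Table 3-2 footnote f says "Randomization must occur after all inclusion and exclusion criteria are met and before the first dose of LUM/IVA", and footnote e puts the blood draw ahead of that dose too. Protocol 11.3.1 states that the bottle reports a dosing time at each opening, so clock times are available.

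**The concern.** The cap is a sensible guard against crediting repeat openings. But the unit to which it is applied appears to be the calendar date, while the protocol's schedule runs on 12-hour intervals with tolerances that can cross midnight. A permitted late evening dose can therefore land on a date that already has its two openings, and the cap then removes a real dose. The first and last dates raise a related problem: each counts as a full day in the denominator even if only one dose could be taken.

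For a subject dosing as the protocol allows, both effects lower the score. That score underlies all four adherence endpoints kept after early termination, including the proportions at or above 80% and 90%.

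**Working it through.** The plan gives no figure for this effect, so there is none to reproduce. The score is 100 × Σ min(openings on the date, 2) / (2 × days), with no interruption days assumed. Over 12 weeks the denominator is 2 × 84 = 168.

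**1. Can a permitted dose fall after midnight?** Yes. Under the 6-hour rule it can when the usual evening time is after 18:00 (for example 20:00 + 6 h = 02:00). Under the 4-hour tolerance it can when the usual evening time is after 20:00.

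**2. One isolated late night.** Date 1 has an opening at 08:00. Date 2 has openings at 00:30, 08:00 and 20:00. Four doses were taken; the score is min(1,2) + min(3,2) = 1 + 2 = 3. The cost is 1/168 = 0.6 points.

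**3. Consecutive late nights.** The first date of the run has one opening, each middle date has two (the previous evening's late dose plus the morning dose), and the date after the last late night has three, capped to two. One count is lost per run, however long.

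**4. Scores over 84 days for a subject who takes every dose** (usual times 08:00 and 20:00; late evening doses at 00:30):

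| Pattern | Counted | Score |
|---|---|---|
| One isolated late night in total | 167/168 | 99.4% |
| One run of ten late nights | 167/168 | 99.4% |
| Every evening dose after midnight | 167/168 | 99.4% |
| One isolated late night a week | 156/168 | 92.9% |
| Two consecutive late nights a week | 156/168 | 92.9% |
| Two separate late nights a week | 144/168 | 85.7% |
| Every second night (worst case) | 126/168 | 75.0% |

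**5. Distance to the cuts.** 0.9 × 168 = 151.2, so 152 counts are needed for 90%, and 168 − 151 = 17 losses put a fully adherent subject below it. 0.8 × 168 = 134.4, so 135 counts are needed for 80%, and 168 − 134 = 34 losses put the subject below it. A subject who truly missed 7 doses (161/168 = 95.8%) and lost one further count a week would read (161 − 12)/168 = 88.7%.

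**6. Plausible size under random timing.** The documents give no usual clock times or timing spread, so these are assumptions: independent normal errors limited to 4 hours, SD 1 to 2 h, every dose taken. Mean 12-week scores:

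- usual evening time 20:00: 100.0% to 98.9% (the lower figure treats doses held at the 4-hour limit, exactly midnight, as falling on the new date)
- 22:00: 98.9% to 93.2%
- 23:00: 93.3% to 89.3%

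The share of these simulated subjects below 90% was 0 to 1.9% at 22:00 and 2.2% to 71.9% at 23:00. None fell below 80%.

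**7. First and last dates.** If only one dose is possible on the first date, the loss is one expected opening: 1/168 = 0.6 points over 84 days, 1/56 = 1.8 over 28 days and 1/28 = 3.6 over 14 days. In the whole-duration endpoint a one-dose last date costs the same again, so 2/28 = 7.1 points at 14 days. The 14- and 28-day exposures are assumed.

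**The case against.** The strongest reply is that the SAP never says midnight. Its words are day and actual date, and the calendar date is an inference. That is fair, but the date arithmetic in the denominators makes it the natural reading, and a different intention would still need to be written down.

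The rest of the case for leaving the rule alone concerns size and consequence. After early termination the analysis is descriptive and no test rests on either cut. Tablet-count compliance in SAP 8.2.6 has no daily cap. At a usual evening time of 20:00 the loss is about a point at most under the assumed timing errors. All of this stands. It limits the importance of the point but does not remove the error.

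Several stronger readings are tempting and are not supported:

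- **That after-midnight doses are discarded as a rule.** They are lost only when the new date has two other openings; a subject who always doses after midnight still scores 99.4%.
- **That a late first dose is scored as missed.** That opening is counted. What is missing is the other expected opening on that date. Nor does a first dose after noon rule out a second that day: if the 4-hour tolerance permits an 8-hour interval, a 13:00 dose can be followed by one from 21:00. No document says how late Day 1 visits run.
- **That two openings are expected on literally every date.** Physician-directed interruption days are removed.
- **That the rule penalizes Arm A.** Protocol Table 8-1 and its text give Arm A reminders of upcoming as well as missed doses. These could produce more late recoveries or fewer late doses, and the documents give no figure for either.

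**Conclusion.** The point holds as a modest, correctable flaw in the derivation. On the calendar-date reading, each isolated run of permitted after-midnight dosing removes one real dose from the score, at 0.6 points each over 12 weeks. A one-dose first date, and in the whole-duration endpoint a one-dose last date, each adds a further shortfall of one opening. For a subject dosing as permitted, these errors only understate intake; that says nothing about the direction of other errors in bottle data.

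The effect is small for most subjects. It becomes material for late-evening or irregular dosers, for subjects close to 80% or 90%, and for short exposures in the whole-duration mean. The weekly figures assume late nights that are isolated from one another, and the simulated ranges rest on assumed clock times and timing spread. A difference between arms is possible, but its direction is unknown.

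**What to change.** In SAP 8.3.2, use the recorded opening times in one of two ways: assign each opening to its scheduled dose, or define the dosing day by a prespecified cut-off in the overnight gap instead of midnight, and apply the cap of 2 within that dosing day. Set the expected openings on the first and last dosing days to the number of scheduled doses inside that same boundary, and cap counted openings at the expected number so that no score exceeds 100%. Use one rule in both arms and both formulas.

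Two details need care.

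- **One clock time for everyone may only move the problem.** With a 03:00 cut-off, a usual 22:00 dose taken 6 hours late (04:00) and a usual 06:00 dose taken 4 hours early (02:00) both cross it. If T is a subject's usual evening time and doses are 12 hours apart, the latest permitted evening dose is T + 6 h and the earliest permitted morning dose is T + 12 − 4 = T + 8 h, so a cut-off such as T + 7 h separates them.
- **Proration must use the same boundary as the count.** Expecting one dose whenever the first opening is after noon, combined with a 03:00 cut-off, would count doses at 13:00 and 01:00 against one expected opening and could give 168/167 = 100.6%.

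No new data are needed, because the bottles already report times. The cost is a slightly longer derivation and a boundary, with the rule for each subject's usual time if one is used, that must be fixed before analysis.
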